## **2.8 Trial Population**

Vaccinia-naïve HIV-infected women and men of any ethnicity aged 18 to 45 years who meet all of the inclusion and none of the exclusion criteria are able to enroll into this trial.

## **2.9 Risk/Benefit Assessment**

### **2.9.1 Potential Risks**

Blood drawing may cause discomfort, bruising or light-headedness. Rarely, a blood draw may result in infection at the site where the blood is taken.

Preclinical data with MVA-BN® in rats and rabbits have revealed no special hazard for humans based on conventional studies of safety.

Based on the available data for MVA-BN® as well as for MVA-based vaccines in healthy and immunocompromised subjects, adverse reactions in this trial setting are expected to be comparable to adverse reactions previously reported for MVA-BN® and/or those typically seen with other modern vaccines. Main risks involve the development of local reactions at the injection site, e.g. erythema, pain swelling and induration.

As with all injectable vaccines, there is a risk of an allergic reaction or an anaphylactic event. Trial site staff will watch subjects for at least 30 minutes after each vaccination and in the event

that a severe allergic reaction might occur, appropriate medical treatment and supervision will be readily available.

The severe and life-threatening adverse reactions such as progressive vaccinia, eczema vaccinatum, generalized vaccinia and inadvertent inoculation that have been observed after the administration of conventional smallpox vaccines are due to the replication of these vaccinia strains. MVA-BN® is replication incompetent in human cells and consequently has a better safety and tolerability profile. It is essentially impossible that MVA-BN® could induce the severe side effects listed above associated with replication competent vaccinia viruses. Apart from the better safety profile with regard to severe reactions, the available clinical experience with MVA-BN® shows that it is generally better tolerated, for example with regard to local reactions, than conventional smallpox vaccines.

## 2.9.2 Benefits

There will be no direct benefit to the trial participants. Trial participants will contribute significantly to the development of a safer smallpox vaccine which is a benefit for society in view of a potential threat following deliberate release of smallpox virus. Based on the current immunogenicity and efficacy data collected in non-clinical and clinical studies, participants in clinical trials are expected to acquire protection against smallpox infection.

Analysis of the samples collected will not directly benefit the subject. BN may learn more about smallpox and other diseases: how to prevent them, how to treat them, or how to cure them.

## 3 Objectives

Please refer to trial protocol synopsis [Section 1.5](#).

## 4 Trial Design

### 4.1 Experimental Design

Randomized, open-label Phase II trial to assess the safety and immunogenicity of MVA-BN® smallpox vaccine when increasing the number of injections compared to the standard regimen in immunocompromised subjects with HIV infection

In total, 90 vaccinia-naïve subjects will be enrolled in this trial (see [Table 4](#)). All subjects will be randomly assigned (1:1:1) to Group 1, Group 2 or Group 3. Group 1 will receive the standard regime – two vaccinations at Day 0 and Day 28. Group 2 will receive two injections at each vaccination day in the standard schedule and Group 3 will receive the standard regime and an additional early boost 12 weeks after the first dose of the standard vaccination schedule with MVA-BN® smallpox vaccine.

**Table 4 Distribution of the Three Treatment Groups**

Groups	N	Dose (TCID 50 ) per Injection (0.5 ml)	Number of Injections	Vaccinations (Weeks)
1	30	at least 1 x 10  /ml	Standard regime	0 - 4
2	30	at least 1 x 10  /ml	Two injections at each time point	0 - 4
3	30	at least 1 x 10  /ml	Standard regime + additional boost	0 - 4 - 12

## 4.2 Description of Trial Procedures

The trial procedures will be conducted according to the trial procedure schedule ([Section 1.6](#)) and as described on the following pages. Visits must be scheduled within the intervals / visit windows given below.

### 4.2.1 Screening Phase

All subjects must be thoroughly informed of all aspects of the trial (e.g. trial visit schedule, required evaluations and procedures, risks and benefits) as described in the informed consent form (ICF). The ICF and the statement about the Health Insurance Portability and Accountability Act (HIPAA) must be reviewed with the subject and signed and dated by the subject and the Investigator, or person designated by the investigator, who conducted the informed consent discussion before proceeding with any evaluations or procedures required by this protocol.

After ICF has been collected, subjects will enter a screening period of up to 28 days before the first vaccination.

Screening Visit (Days -28 to -1)

The following tasks will be performed
 
 
• Subject to read, sign and date ICF and HIPAA
 
• Check inclusion/exclusion criteria
 
• Obtaining medical history
 
• Obtaining HIV specific medical history
 
• Check vaccination history (previous smallpox vaccination or vaccination with a pox-virus-based vaccine) and absence of smallpox vaccination scar
 
• Complete physical examination including auscultation of heart and lungs and measurement of body weight and height
 
• Evaluation of vital signs
 
• Cardiac assessment (Section 8.2.7) 
 
○ Calculation of the individual cardiac risk factor (after receipt of lab results for cholesterol)
 
○ Evaluation of family cardiac risk factors
 
○ Perform baseline ECG
 
 
 
• Recording of AEs/SAEs/AESIs
 
• Recording of prior and concomitant medication
 

- Counseling on avoidance of pregnancy: Review of acceptable contraceptive methods and recent menstrual history with WOCBP
- Blood draw (2 ml) for CD4 count
- Blood Draw (4 ml) for viral load
- Blood draw for safety laboratory (7 ml) including
  - Serum pregnancy test (WOCBP only)
  - Hematology & serum chemistry
  - Troponin I
  - Total cholesterol, High-density Lipoprotein (HDL) and Low-density Lipoprotein (LDL)

If a subject is screened and cannot be enrolled, because of a certain transient condition (e.g. abnormal lab value due to an acute condition or a missing lab evaluation due to mishandling of the sample), then the subject can be re-screened on one further occasion only and the respective test(s) should be repeated as a “partial” re-screening rather than a full re-screening. The re-screening visit must be within the 28 day window started by the first screening visit and the window -28 to -1 before first vaccination must not be exceeded. A “partial” re-screening visit is indicated by filling out only the respective re-screening sections in the electronic Case Report Form (eCRF).

If a subject cannot be enrolled due to other circumstances (e.g. completion of a wash-out period for a medication or vaccine not allowed during the trial) or the 28 day period is exceeded, a complete re-screening assessment including physical examination, lab examination, and ECG must be performed. The clock then re-starts at the re-screening visit with Day -28 before the first vaccination.

#### 4.2.2 Active Trial Phase

After successfully passing the screening evaluations, the eligible volunteers can enter the active trial phase (Visit 1 to Visit 5 for Group 1 and Group 2 / Visit 1 to Visit 8 for Group 3) starting with Visit 1.

At Visit 1 subjects will be assigned randomly to Group 1, Group 2 or Group 3 after re-confirmation of the subject’s eligibility. The randomization scheme is 1:1:1 (Group 1, 2, 3). An automated randomization system will be used. The detailed process will be described in a trial specific procedure.

The procedures performed at Visit 1 and all following visits are listed below. **Blood draws and all other examinations listed above the vaccination events must always be performed prior to vaccination.**

At Visit 1 / Day 0, subjects will receive the first s.c. vaccination with 0.5 ml of MVA-BN® in the upper arm.

Following each vaccination subjects will be kept under close observation at the clinical trial site (CTS) for at least 30 minutes, with appropriate medical treatment readily available in case of a

rare anaphylactic reaction following the administration of vaccines. Any AEs that occur during or after vaccination will be recorded.

Reactogenicity and AEs will be collected on a subject memory aid by having the subject record local and general symptoms for an 8-day period (Days 0-7), beginning with the day of vaccination. The memory aid will be returned to the clinic staff at the following visit. If symptoms persist at Day 7, daily symptoms and temperature will continue to be measured each day until resolved and the last day of symptoms and maximum intensity is recorded on the memory aid. Unsolicited AEs will be assessed at all visits except FU 1 and FU 2 (Screening to Visit 5 for Group 1 and 2 / Screening to Visit 8 for Group 3).

### Visit 1 (Day 0)

#### **Tasks to be performed prior to randomization and vaccination**

- Confirmation of inclusion / exclusion criteria
- Targeted physical examination including auscultation of the heart and lungs
- Evaluation of vital signs
- Recording of AEs/SAEs/AESIs
- Recording of concomitant medications
- Counseling on avoidance of pregnancy: Review of acceptable contraceptive methods and recent menstrual history with WOCBP
- Urine pregnancy test (WOCBP only)
- Blood draw (9 ml; serum collection) for immunogenicity testing (baseline)

**If the subject is still eligible for participation in this trial the subject will be randomized.**

#### **The following tasks will be performed after randomization:**

- Administration of first MVA-BN® vaccination
- Subject observation by CTS staff for at least 30 minutes after vaccination
- Recording of immediate AEs/AESIs/SAEs
- Handout of memory aid for first vaccination, ruler and thermometer

Temporary deferral of vaccination: If an acute illness is present the subject may be vaccinated at a later date within the accepted time window. The vaccine can be administered to persons with a minor illness such as diarrhea, mild upper respiratory infection, or any other mild condition with or without low-grade febrile illness, i.e. oral temperature < 100.4°F (< 38.0°C).

**Visit 2 (V1 + 12-16 days)**

**The following tasks will be performed**

- Targeted physical examination including auscultation of the heart and lungs
- Evaluation of vital signs
- Performing of ECG
- Recording of concomitant medication
- Recording of AEs/SAEs/AESIs
- Blood draw (2 ml) for CD4 count
- Blood Draw (4 ml) for viral load
- Blood draw (7 ml) for safety laboratory including
  - Troponin I
  - Hematology & serum chemistry
- Collection of the memory aid handed out at Visit 1, review with subject
- Examination of the vaccination site(s)

**Visit 3 (V1 + 28-35 days)**

**Tasks to be performed prior vaccination**

- Check withdrawal criteria (see [Section 4.2.5](#))
- Targeted physical examination including auscultation of the heart and lungs
- Evaluation of vital signs
- Recording of concomitant medications
- Counseling on avoidance of pregnancy: Review of acceptable contraceptive methods and recent menstrual history with WOCBP
- Recording of AEs/SAEs/AESIs
- Urine pregnancy test (WOCBP only)
- Blood draw (9 ml; serum collection) for immunogenicity testing

**If the subject is still eligible to receive the second vaccination the following tasks will be performed**

- Administration of second MVA-BN® vaccination
- Subject observation by CTS staff for at least 30 minutes after vaccination
- Recording and documentation of immediate AEs/SAEs/AESIs
- Handout of the memory aid for second vaccination

Temporary deferral of second vaccination: If an acute illness is present the subject may be vaccinated at a later date within the accepted time window. The vaccine can be administered to persons with a minor illness such as diarrhea, mild upper respiratory infection, or any other mild condition with or without low-grade febrile illness, i.e. oral temperature < 100.4°F (< 38.0°C).

**Visit 4 (V3 + 12-16 days)**

**The following tasks will be performed**

- Targeted physical examination including auscultation of the heart and lungs
- Evaluation of vital signs
- Recording of concomitant medication
- Recording of AEs/SAEs/AESIs
- Blood draw (2 ml) for CD4 count
- Blood draw (7 ml) for safety laboratory including
  - Hematology & serum chemistry
  - Troponin I
- Blood draw (9 ml; serum collection) for immunogenicity testing
- Collection of the memory aid handed out at Visit 3, review with subject
- Examination of the vaccination site(s)
- 

**Only if clinically indicated**

- Perform ECG reading

**Visit 5 (V3 + 28-35 days)**

**The following tasks will be performed**

- Targeted physical examination including auscultation of the heart and lungs
- Evaluation of vital signs
- Recording of concomitant medication
- Recording of AEs/SAEs/AESIs
- Urine pregnancy test (WOCBP)

**Group 3 only: Visit 6 (V1 + 84-96 days)**

**Tasks to be performed prior to vaccination**

- Check withdrawal criteria (see [Section 4.2.5](#))
- Targeted physical examination including auscultation of the heart and lungs
- Evaluation of vital signs
- Recording of concomitant medications
- Counseling on avoidance of pregnancy: Review of acceptable contraceptive methods and recent menstrual history with WOCBP
- Recording of AEs/SAEs/AESIs
- Urine pregnancy test (WOCBP only)
- Blood draw (9 ml; serum collection) for immunogenicity testing

**If the subject is still eligible to receive the booster vaccination the following tasks will be**

**performed**

- Administration of booster MVA-BN® vaccination
- Subject observation by CTS staff for at least 30 minutes after vaccination
- Recording and documentation of immediate AEs/SAEs/AESIs
- Handout of the memory aid for booster vaccination

Temporary deferral of booster vaccination: If an acute illness is present the subject may be vaccinated at a later date within the accepted time window. The vaccine can be administered to persons with a minor illness such as diarrhea, mild upper respiratory infection, or any other mild condition with or without low-grade febrile illness, i.e. oral temperature < 100.4°F (< 38.0°C).

**Group 3 only: Visit 7 (V6 + 12-16 days)**

**The following tasks will be performed**

- Targeted physical examination including auscultation of the heart and lungs
- Evaluation of vital signs
- Recording of concomitant medication
- Recording of AEs/SAEs/AESIs
- Blood draw (2 ml) for CD4 count
- Blood draw (7 ml) for safety laboratory including
  - Hematology & serum chemistry
  - Troponin I
- Blood draw (9 ml; serum collection) for immunogenicity testing
- Collection of the memory aid handed out at Visit 6, review with subject
- Examination of the vaccination site

**Only if clinically indicated**

- Perform ECG reading

**Group 3 only: Visit 8 (V6 + 28-35 days)**

**The following tasks will be performed**

- Targeted physical examination including auscultation of the heart and lungs
- Evaluation of vital signs
- Recording of concomitant medication
- Recording of AEs/SAEs/AESIs
- Urine pregnancy test (WOCBP only)
- Blood draw (2 ml) for CD4 count

### 4.2.3 Follow-Up (FU) Phase

To monitor long-term safety, subjects will come six months (FU 1) after the last vaccination and 12 months after the last vaccination (FU 2) to the CTS. It will be checked if an SAE/AESI has occurred since the last trial visit and if there is any new information on SAEs/AESIs/AEs ongoing at last trial visit. A targeted physical examination, evaluation of vital signs and a blood draw for immunogenicity and CD4 count will be done.

#### 4.2.3.1 FU 1

For subjects who were withdrawn from the second MVA-BN® vaccination, the FU 1 will be performed six months after the 1st vaccination and for subjects who were withdrawn from the booster MVA-BN® vaccination, the FU 1 will be performed six months after the 2nd vaccination (see [Section 4.2.5](#)).

FU 1 (V3 + 182-210 days for Group 1 and 2 / V6 + 182-210 days for Group 3)

The following tasks will be performed
 

• Recording of SAEs/AESIs and AEs ongoing at last active trial visit (Visit 5 for Group 1 and 2, Visit 8 for Group 3).

• Targeted physical examination including auscultation of the heart and lungs

• Evaluation of vital signs

• Blood draw (9 ml; serum collection) for immunogenicity testing

• Blood draw (2 ml) for CD4 count

 
Only if clinically indicated
 

• Blood draw for safety laboratory (7 ml)

• Other safety evaluations, if required

#### 4.2.3.2 FU 2

For subjects who were withdrawn from the second MVA-BN® vaccination, the FU 2 will be performed 12 months after the 1st vaccination and for subjects who were withdrawn from the booster MVA-BN® vaccination, the FU 2 will be performed 12 months after the 2nd vaccination (see [Section 4.2.5](#)).

FU 2 (V3 + 364-392 days for Group 1 and 2 / V6 + 364-392 days for Group 3)

The following tasks will be performed
 

• Subject to read, date and sign updated ICF (adding FU 2 to the original trial schedule)

• Recording of SAEs/AESIs and AEs ongoing at last active trial visit.

• Targeted physical examination including auscultation of the heart and lungs

• Evaluation of vital signs

• Blood draw (9 ml; serum collection) for immunogenicity testing

• Blood draw (2 ml) for CD4 count

 
Only if clinically indicated
 

• Blood draw for safety laboratory (7 ml)

• Other safety evaluations, if required

#### 4.2.4 Unscheduled Visits

If clinically indicated, additional visits may be necessary between scheduled visits. Unscheduled visits may be performed to repeat laboratory testing or physical exams due to a new development. Examinations, performed at unscheduled visits will be documented in the source documents as well as in the respective eCRF sections for unscheduled visits.

#### 4.2.5 Withdrawal from Second or Booster Vaccination

The decision not to administer the second/booster vaccination can be made by the investigator or by the subject.

##### Criteria:

The following criteria should be checked prior to second/booster vaccination. If any are applicable, the subject should not receive any further vaccination(s):

- Any clinically significant cardiac sign and symptom (i.e. AESI) defined in [Section 8.1.2.3](#).
- An AE that, in the opinion of the investigator, makes it unsafe for the subject to receive a further vaccination. In this case, the appropriate measures will be taken.
- Anaphylactic reaction following the administration of any vaccine(s).
- Clinical need for concomitant or ancillary therapy not permitted in the trial, i.e.
  - Vaccination with any licensed live vaccine within 30 days prior or after trial vaccinations or any licensed killed vaccine within 14 days prior or after trial vaccinations
  - Start of chronic systemic administration (defined as more than 14 days) of > 5 mg prednisone (or equivalent) per day or any other systemic use of immune-modifying drugs.
  - Administration of immunoglobulins and/or any blood products.
- Use of any investigational or non-registered drug or vaccine other than the trial vaccine.
- Pregnancy
- Subject refuses to receive second vaccination.
- Any condition which contradicts administration of the second vaccination in the opinion of the investigator.

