### **8.1.2.3 AESIs**

An AESI is defined in this trial as:

- Any cardiac sign or symptom developed since the first vaccination
- ECG changes determined to be clinically significant
- Cardiac enzyme troponin I  $\geq 2 \times$  ULN

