### **8.2.7 Cardiac Assessment**

To evaluate the cardiac profile of MVA-BN®, targeted physical exams including auscultation of the heart and lung will be performed ([Section 8.2.3](#)). Any kind of cardiac signs (i.e. discovered by the physician during examination of the patient) or symptom(s) (i.e. experienced and reported by the subject) detected during the trial such as but not limited to chest pain, dyspnea, arrhythmia or edema are recorded.

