### Troponin I

Troponin I will be measured at SCR and on the following visits: Visit 2, Visit 4 and Visit 7 (Group 3 only).

Cardiac events fulfill the definition of an AESI as described in [Section 8.1.2.3](#). The investigator will be asked to assess the clinical significance of the case.

Case definitions as published by the CDC ([Morbidity and Mortality Weekly Report \[MMWR\] May 30, 2003](#)) are provided in [Section 16.2](#); [Appendix II: Case Definitions Acute Myocarditis / Pericarditis](#) in order to:

[figure not shown]
- help investigators to recognize possible events of acute myocarditis and/or pericarditis and
- distinguish from unspecific and isolated ECG changes without or with unclear clinical significance.

Subjects who develop any kind of cardiac signs or symptoms during the trial such as but not limited to chest pain, dyspnea, arrhythmia or edema are referred to a local cardiologist for cardiac evaluation such as (treadmill) ECG, measurement of cardiac enzyme and/or echocardiogram. Depending on the results of these evaluations, further diagnostic tests will be done as recommended by the cardiologist and subjects will be followed up at a frequency determined by the cardiologist. Any AESIs occurring after at least one vaccination will be followed up until complete resolution or until the sequelae are stable and considered to be permanent.

In any case of cardiac signs or symptoms, or increased laboratory results for Troponin I, the subject will be asked to attend for an unscheduled visit at the site, in order to perform or repeat Troponin I testing, to perform a physical examination for cardiac symptoms and to record an unscheduled ECG.

Further details regarding the follow-up of AESIs are described in the ‘Investigator’s Manual – Follow-up of Adverse Events of Special Interest’.

[Figure 1](#) outlines the algorithm for assessment of cardiac events.

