#### 3.2.2 Per Protocol Set (PPS)

This is the subset of subjects in the FAS who have received all vaccinations, completed all visits of the active trial phase (Visit 1 to Visit 5 and additionally Visit 6 to Visit 8 for Group 3; see [Table 1](#)) and adhered to all protocol conditions. Subjects with only minor (not relevant) protocol deviations are included into this dataset.

The decision whether a protocol deviation is major or not will be made on a case-by-case basis in a data review meeting (DRM) prior to database lock.

Examples of major protocol violations are:

1. Premature discontinuation of the trial before Visit 5 for Groups 1 and 2 or Visit 8 for Group 3 (the question “prematurely terminated the trial?” is answered with “yes” even where no other reason exists to exclude the subject from further participation in accordance with the protocol)
2. Subject did not meet all of the inclusion criteria
3. Subject met one or more of the exclusion criteria
4. Withdrawal from the second and/or third vaccination

- 
5. Major vaccine preparation and administration deviation from specification as given in the protocol including cases where the subject fulfils at least one of the criteria specified in the protocol for withdrawal from vaccination
  6. Major deviations of the visit window as determined during the DRM(s)
  7. Unallowed prior or concomitant medication
  8. Missing humoral immune response data (ELISA and PRNT) at Visit 1 or 4 (or Visit 7 for Group 3)

A classification of all subjects in the FAS for major protocol deviations will be performed at the time of the DRM.

The main analysis of the immunogenicity endpoints will be performed on the PPS. The same statistical procedures will also be applied to the FAS.

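### Protocol 4.2.5 stops vaccination for clinically significant cardiac events but cites an AESI definition that covers any cardiac sign or symptom, so a non-significant sign gets two answers

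*Protocol*

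**What the plan says.** **Withdrawal criterion.** Protocol Section 4.2.5 lists conditions to check before the second and booster vaccinations. A subject to whom any of them applies should not be vaccinated again. The first condition is "Any clinically significant cardiac sign and symptom (i.e. AESI) defined in" Section 8.1.2.3.

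**AESI definition.** Protocol Section 8.1.2.3 has three items: "Any cardiac sign or symptom developed since the first vaccination"; "ECG changes determined to be clinically significant"; and troponin I at or above 2 x ULN.

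**Cardiac assessment.** Protocol Section 8.2.7 casts a wide net: signs and symptoms of any kind "detected during the trial such as but not limited to chest pain, dyspnea, arrhythmia or edema are recorded". Under its Troponin I heading it says that cardiac events meet the AESI definition, and then: "The investigator will be asked to assess the clinical significance of the case".

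**Analysis set.** SAP Section 3.2.2 gives examples of major protocol violations. Item 4 is "Withdrawal from the second and/or third vaccination". Item 5 covers major deviations in vaccine preparation and administration, among them cases where "the subject fulfils at least one of the criteria specified in the protocol for withdrawal from vaccination". The PPS carries the main immunogenicity analysis, and the same procedures are repeated on the FAS.

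**The concern.** The abbreviation i.e. in 4.2.5 asserts that clinically significant cardiac signs and symptoms and AESIs are the same events. The definition it cites is wider. An investigator who follows the words of 4.2.5 and one who follows the cross-reference could decide differently about the next vaccination for the same finding. The trial is open-label and may use up to 10 sites, so the decision is made locally with the group known.

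There is a second, analytical consequence. The SAP takes the protocol's withdrawal criteria as a reference point for the PPS, so an ambiguity in the criterion carries over into the population for the main immunogenicity comparison. Group 3 is checked against the criteria twice (Visits 3 and 6) and Groups 1 and 2 once (Visit 3), so any effect need not be equal across groups.

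**Working it through.** No figure in the plan is in dispute. The check compares the texts.

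**Step 1. Where the two sets differ.**

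| Event before a second or booster vaccination | AESI under 8.1.2.3? | Covered by the wording of 4.2.5 without its cross-reference? |
|---|---|---|
| Cardiac sign or symptom, judged clinically significant | Yes | Yes |
| Cardiac sign or symptom, judged not clinically significant | Yes | No |
| ECG change, clinically significant | Yes | Broadly yes; significance is required in both places |
| ECG change, not clinically significant | No | No |
| Isolated troponin I at or above 2 x ULN | Yes | Unclear; a laboratory value is not plainly a sign or symptom |

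The second row is the contradiction. The last row is secondary: 8.2.7 describes signs as found by the physician on examination and symptoms as reported by the subject, which does not fit a laboratory value, but the cross-reference brings troponin in.

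**Step 2. Whether non-significant AESIs can exist.** They can. Section 8.2.7 establishes AESI status first and asks about significance afterwards. The second row is therefore a category that the protocol itself creates.

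**Step 3. What follows for the PPS.** Take a subject in the second row.
- *Any AESI stops vaccination.* If the subject is withdrawn, SAP item 4 applies. If the subject is vaccinated, item 5 applies. Both are listed examples of major violations.
- *Only clinically significant events stop vaccination.* The subject is vaccinated, the cardiac criterion is not met, and the subject can stay in the PPS.

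**Step 4. Sensitivity, on assumed losses only.** Inputs from Protocol 9.2: 30 per group, a difference of 0.74 SD, a two-group t-test at 5% two-sided, 80% power. Power is the probability that a noncentral t variable with 2n − 2 degrees of freedom and noncentrality 0.74 × √(n/2) exceeds the two-sided critical value in absolute size. At n = 30 the noncentrality is 0.74 × √15 = 2.87 and power is 80.5%, which reproduces the plan's figure. If each group lost subjects from the PPS:

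| Assumed loss per group | n per group | Power |
|---|---|---|
| 0 | 30 | 80.5% |
| 1 | 29 | 79.1% |
| 2 | 28 | 77.6% |
| 3 | 27 | 76.1% |
| 4 | 26 | 74.4% |
| 6 | 24 | 70.9% |

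**Step 5. Unequal exposure, again on an assumption.** The last vaccination falls at about day 28 in Groups 1 and 2 and about day 84 in Group 3. With a constant rate, a proportion p affected by day 28 becomes 1 − (1 − p)^(84/28) = 1 − (1 − p)³ by day 84. For p = 2%, 5% and 10% this gives 5.9%, 14.3% and 27.1%. These values of p are not estimates. They show only that PPS loss through this criterion could be larger in Group 3.

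**The case against.** **The data review meeting can settle it.** SAP 3.2.2 offers its items as examples and leaves major or minor to a case-by-case decision before database lock. That is a trial-level step, so one reading could be applied to all sites. This stands, and it means PPS exclusion is not automatic. But neither document tells the meeting which reading governs, and the meeting cannot reverse a vaccination already given or withheld.

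**The FAS is a safeguard.** The main safety analysis uses the FAS and immunogenicity is repeated on it. FAS membership needs one injection and any data, so it does not turn on this criterion. This stands, and it confines the analysis-set effect to the main immunogenicity analysis.

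**The safety side has other cover.** Two further items in 4.2.5 let the investigator withhold vaccination by judgement. Section 8.2.7 requires an unscheduled visit for cardiac signs, symptoms or raised troponin, and cardiology referral for signs and symptoms. This softens the consequence but does not say whether a non-significant AESI must stop vaccination.

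**Other documents may answer it.** The text available for this check does not reproduce the cardiac algorithm in Protocol Figure 1, and the Investigator's Manual on AESI follow-up is a separate document. Either might address further vaccination. Divergence between sites is therefore possible rather than shown.

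**A number might be inferred from Protocol Table 1.** It lists increased troponin I as a common adverse drug reaction (at least 1/100 and below 1/10). Thirty subjects times 1% to 10% is 0.3 to 3 per group. The documents do not support using this as the number affected. The entry has no 2 x ULN threshold, pools completed trials (N = 3,445), counts only suspected reactions and is not limited to the time before a later vaccination. It also concerns troponin, which is not where the main conflict lies.

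**Conclusion.** Wrong as written: an internal contradiction between Protocol 4.2.5 and the definition it cites. For a cardiac sign or symptom judged not clinically significant, the documents give two answers on whether vaccination stops. The troponin item is a lesser uncertainty of wording.

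The reading can affect PPS membership through SAP 3.2.2 items 4 and 5. A reader might infer that the same subject is in or out of the PPS on the reading alone, or that the primary safety result is compromised. Neither follows, given the case-by-case data review and the use of the FAS for safety.

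The size cannot be stated, because the documents give no AESI rate. The power and exposure figures above rest on assumed losses and an assumed constant rate, and are illustrations only.

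**What to change.** Reconcile Protocol 4.2.5, 8.1.2.3 and 8.2.7 so that the withdrawal criterion and the definition it cites name the same set of events. State explicitly how a cardiac sign or symptom judged not clinically significant is handled, and how an isolated troponin I at or above 2 x ULN is handled. Which set is right is a clinical decision for the sponsor. Check that Figure 1 and the Investigator's Manual agree with the wording chosen.

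Point SAP 3.2.2 item 5 to that wording, so that the data review meeting applies one reading to all sites and groups.

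The cost is one protocol clarification and one SAP cross-reference. The sample size and the analysis methods do not change.
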